8.8 PATIENT-REPORTED OUTCOMES RESEARCH

Participants enrolled in the prostate cancer cohort may be offered the option to use ApricityCare™, a patient-reported outcome (PRO) digital application, during their participation in this study. Study staff will have an opportunity to review participant's data at the ApricityOncology™, a clinical dashboard website.

The ApricityCare™ smartphone app allows participants (or their designee) to self-report adverse events in between clinic visits. The app also provides educational information and videos about potential AEs participants may experience. ApricityCare™ was initially developed for the identification and management of irAEs in participants receiving standard-of-care immunotherapy for cancer.

Inclusion of the technology in the current PICI0025 AMADEUS prostate cancer cohort will generate important data on the feasibility of incorporating this approach to PRO collection in a clinical research setting. Participation in this research is optional for study participants, and the use of ApricityCare™ will not impact the participant's treatment and is not a substitute for clinical evaluation. The data collected via this app for participants as well as the ApricityOncology app for the study team is for exploratory research purposes only and will not be incorporated in the PICI0025 electronic data capture system. In the event of AEs or SAEs that meet reporting criteria per [Section 8.3](#), providers and study team members will continue to follow reporting procedures per [Section 10.5](#). The de-identified data collected via ApricityCare™ and ApricityOncology may be used by Sponsor's researchers and its affiliates, Apricity Health, and/or shared with other researchers and/or institutions for use in future research.

The clinician-facing portion of this application will produce recommendations for irAE management as advisory to clinicians and investigators. The management guidelines will use algorithms and the toxicity management guidelines from [Table 7](#). These do not constitute Medical Advice and will not be presented directly to participants.

8.8.1 Medical Disclaimer

The ApricityCare™ app does not make any medical diagnosis, does not provide any treatment, and does not substitute medical service or communication with a healthcare provider. The software used in this patient-reported study is intended for research purposes only.

All content found on the ApricityCare™ app, including text, images, audio, or other formats, are only for research. If Medical Assistance is needed, participants are instructed via the ApricityCare™ app to call 911 and alert their health care provider.

8.8.2 Health Data Protection

Participant's medical information obtained by the AMADEUS study and this optional procedure is confidential. It may be disclosed to third parties only as permitted by the ICF (or separate authorization for use and disclosure of personal health information) signed by the participant or as permitted or required by law.

Apricity will provide training to site staff. PICT's monitors will not have access to the data collected by ApricityCare™ and will not monitor, interfere with or evaluate Apricity's data collection or procedures.

Participants will be registered and receive instructions and training to use the application via the site-level research team. Consenting participants will be requested to download a software application into their smartphone devices. Devices will not be provided. Participants are expected to start using the app daily from the time of informed consent until the safety period to track daily routine and self-monitoring of symptoms. During the participant's end of treatment visit, they will be asked to survey their experience using the ApricityCare™ app.

Throughout the study, the research staff are encouraged to follow the study procedures, in addition to those included in the SOA of this protocol and are not limited to:

- On-boarding to register and train participants in the use of the ApricityCare™ app.
- Reviewing participant's data via ApricityOncology™, a clinical dashboard website at regular intervals per training materials.

Definitions	
ApricityCare™	A smartphone digital application designed for collection of patient-reported assessments.
ApricityOncology™	A clinical dashboard website available for study staff to review participant's data.

8.9 MEDICAL RESOURCE UTILIZATION AND HEALTH ECONOMICS

This section is not applicable.

9 STATISTICAL CONSIDERATIONS

9.1 SAMPLE SIZE DETERMINATION

A total of up to approximately 200 participants with varying tumor types will be enrolled. Enrollment to initial biopsy may be about 10% higher (ie, approximately 220 participants) to account for unexpected challenges obtaining CD8 infiltration information. The selection of 200 participants is to have sufficient numbers in the CD8 high and CD8 low tumor groups in larger tumor populations to report subgroup response rates, the transformation from CD8 low to high, as well as to predict response from marker and clinical information. With 200 participants, approximately 40 and 160 participants are estimated for the CD8 high and CD8 low tumor groups, respectively (Figure 7). Clinical benefit rate (CBR) within tumor groups is expected to range from 10% to 30% (Nivolumab IB). An average CBR of 20% is assumed to provide approximately 32 participants with clinical benefit in the CD8 low tumor group. With 160 participants, a 95% credible interval of CBR with 32 responders would be (14.2%, 26.5%) assuming a beta(0.4, 1.6) prior. Similarly, if there are 30 participants in the largest disease subgroup, a 95% credible interval of response would be (8.3%, 35.2%) assuming 6 responders and a similar prior. There is no prior for the expected proportion of participants who will convert from CD8 low to CD8 high on treatment as this is a first look for this endpoint. The 95% credible interval for 16/160 (10%) participants converting would be (5.9%, 15.1%) and for 80/160 (50%) the credible interval would be (42.3%, 57.7%). Similarly, 8 of 40 participants are in the CD8 high group expected to exhibit benefit, resulting in a 95% credible interval of (9.5%, 33.2%). The selection of 200 participants allows a minimum reasonable number for estimating CBR in the CD8 high tumor group. For secondary analyses, if there are 20 responders in any CD8 status and/or tumor site group, it would be reasonable to perform multivariate logistic regression with 2 variables to predict response. Therefore, 200 participants is the smallest reasonable sample size for the initial exploration of efficacy prediction in this population.

Additional widths of credible intervals of CBR for possible subgroup sizes are presented in [Table 11](#).

Table 11: Possible Subgroup Sizes

Subgroup Size	Clinical Benefit Rate	Expected Success	95% Credible Interval
160	10	16	(6.0, 15.2)
125	10	12	(5.3, 15.5)
100	10	10	(5.1, 16.7)
75	10	8	(5.0, 18.7)
50	10	5	(3.7, 19.9)
40	10	4	(3.2, 21.2)
30	10	3	(2.6, 23.2)
160	20	32	(14.2, 26.5)
125	20	25	(13.5, 27.4)
100	20	20	(12.9, 28.3)
75	20	15	(11.9, 29.6)
50	20	10	(10.4, 31.8)
40	20	8	(9.5, 33.2)
30	20	6	(8.3, 35.2)
160	30	48	(23.1, 37.1)
125	30	38	(22.6, 38.5)
100	30	30	(21.4, 39.0)
75	30	22	(19.6, 39.6)
50	30	15	(18.1, 42.6)
40	30	12	(16.9, 44.0)
30	30	9	(15.2, 46.0)

A total of approximately 20 advanced prostate cancer participants with CD8 low tumors will be treated with the combination of nivolumab and ipilimumab, in 1 of 2 dosing cohorts. The first 10 participants enrolled will be randomly allocated by the Sponsor into one of two cohorts (5 participants per cohort) to evaluate the safety of different dose levels of ipilimumab in combination with nivolumab. If the higher dose level (ipilimumab 5 mg/kg + nivolumab 1 mg/kg) is determined to be tolerable per [Section 6.6.1.4](#), an additional 10 participants will be enrolled at this higher dose level (Prostate Cohort B). If the safety profile of Prostate Cohort B is deemed unacceptable, an additional 10 participants will be enrolled at the lower dose level (Prostate Cohort A).

We hypothesize that higher doses of ipilimumab will demonstrate a larger proportion of participants who convert from CD8 low to CD8 high. There is no prior for the expected proportion of participants who will convert from CD8 low to CD8 high at the various dose levels of ipilimumab. With 15 participants enrolled in Prostate Cohort B, Table 12 provides 95% credible intervals for possible CD8 conversion rates in the cohort. For example, a 95% credible interval assuming 6/15 (40%) participants converting in the cohort would be (17.7%, 64.9%).

Table 12: Credible Intervals for CD8 Conversion

Subgroup Size	CD8 Conversion Rate	Expected Successes	95% Credible Interval
15	20	3	(4.7, 42.8)
15	40	6	(17.7, 64.9)
15	60	9	(35.1, 82.3)

9.2 POPULATIONS FOR ANALYSIS

For purposes of analysis, the following populations are defined (Table 13):

Table 13: Populations for Analysis

Population	Description
Safety Population	All participants who received at least one dose of study drug. Participants will be analyzed according to the study intervention actually received.
Modified Intent-to-Treat (mITT) Population	All participants with sufficient biopsy results to be assigned to a treatment arm and who received at least 1 dose of study drug. Participants will be analyzed according to the study intervention to which they were assigned.
On-treatment Biopsy Population	All participants with at least 1 on-treatment biopsy with sufficient CD8 results will be included in the analyses of changes in CD8 counts

9.3 INTERIM ANALYSES

9.3.1 Safety and Futility Monitoring

Ongoing monitoring for safety and futility will be implemented based on the method of Thall and colleagues (Thall et al, 1995) separately in the CD8 high and CD8 low tumor groups for advanced metastatic cancer and advanced prostate cancer participants. Monitoring will be ongoing during enrollment in each group, once a participant receives treatment and their first treatment biopsy is performed. Screening and accrual to each group will continue until sufficient

information is available to assess the stopping rules as defined below. Stopping rules and operating characteristics were calculated using Multic Lean v2.1.

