9.3.1.1 Safety Monitoring

For trial monitoring and decisions about future trials, TOX criteria are defined in [Section 8.3.7](#). A participant who voluntarily leaves the trial for any reason, including toxicity that does not meet the TOX criteria, will not count as having a TOX. Denote the probability of TOX by θ_T . The stopping rule for advanced metastatic cancer arms is given by the following probability statement: $\Pr(\theta_T > 0.40 \mid \text{data}) > 0.975$. That is, the trial will be stopped if, at any time during the study, it is determined that there is > 97.5% chance that the TOX rate is > 40%. The stopping rules assume a constant TOX rate for “standard therapy” of 0.40 ([Larkin et al, 2015](#); [Wolchok et al, 2017](#)) and a prior $\theta_T \sim \text{beta}(0.8, 1.2)$ for the current study. The stopping boundaries for this toxicity rule are to terminate the trial if the number of participants with TOX compared to the number of participants having received treatment exceeds the limits in [Table 14](#).

Table 14: Rules for Safety and Futility Monitoring per Arm

If there are this many (or more) participants evaluable for response	Stop the arm if there are this many (or more) participants with a TOX event:	Stop the arm if there are this many (or fewer) participants who meet the definition of success defined above:
20	13	1
40	23	3
60	32	6
80	41	9
100	50	12
120	59	15
140	68	19

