9.3.1.2 Futility Monitoring

For trial monitoring, “success” will be defined separately by tumor group. For participants with CD8 low tumors, participants will be counted as having success if they meet the definition of CBR *or* if the tumor converts from CD8 low to CD8 high expression. For participants in the CD8 high tumor group, participants will be counted as success if they meet the definition of CBR. Denote the probability of success by θ_s . We assume $\theta_s \sim \text{beta}(0.4, 1.6)$. The stopping rule is given by the following probability statement: $\Pr(\theta_s < 0.20 \mid \text{data}) > 0.975$. That is, participant enrollment for advanced metastatic cancer arms will be stopped if, at any analysis time, it is determined that there is > 97.5% chance that the CBR is < 20%, a constant rate that is at the average expected response rate for these participants. The stopping boundaries for this futility

rule, shown in [Table 14](#), are designed to terminate enrollment on the arm if the number of overall responses compared with the number of participants enrolled who are evaluable does not meet the requirements of this table. A participant is evaluable for benefit either on the date of disease assessment or the date the participant goes off study without benefit or if the participant does not receive the scheduled disease assessment within 3 weeks without associated scheduling delay. Monitoring will be carried out during enrollment in each advanced metastatic cancer arm. Participants who withdraw from the study after receiving treatment but before undergoing on-treatment biopsies or who miss the evaluation window without associated treatment delay will be counted as not benefitting and therefore evaluable for analysis. CBR is defined as best response of CR or partial response (PR) any time or stable disease (SD) lasting 6 months. For futility monitoring purposes, confirmation of response (CR or PR) is not required. Additionally, a participant who has been on study between 12 weeks and 6 months and has SD at the time of data collection will be counted as a success for that futility analysis. If that participant later progresses and no longer meets the SD definition, their updated information will be included in the monitoring analysis ([Table 14](#)).

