#### 5.9 Interim Analyses

Ongoing monitoring for safety and futility will be implemented based on the method of Thall and colleagues (Thall et al, 1995) separately in the CD8 high and CD8 low tumor groups for advanced metastatic cancer and advanced prostate cancer participants. Monitoring will be ongoing during enrollment in each group, once a participant receives treatment and their first treatment biopsy is performed. Screening and accrual to each group will continue until

sufficient information is available to assess the stopping rules as defined in the protocol Section 9.3.

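### Protocol 9.3.1 and SAP 5.9 extend Thall-method safety and futility monitoring to prostate participants, but the rules cover metastatic arms only; prostate combination cohorts have separate safety rules, and prostate has no futility rule

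*Protocol*

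**What the plan says.** **Scope.** Protocol 9.3.1 applies the monitoring "separately in the CD8 high and CD8 low tumor groups for advanced metastatic cancer and advanced prostate cancer participants" and refers the reader to the rules that follow it. SAP 5.9 gives the same scope, the "tumor groups for advanced metastatic cancer and advanced prostate cancer participants", and defers to Protocol 9.3 for the rules. Protocol 9.4 adds that on-treatment data will guide conclusions on success or futility for every combination and subpopulation.

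**Rules.** Protocol 9.3.1.1 begins its toxicity criterion with "The stopping rule for advanced metastatic cancer arms is given by the following probability statement". Protocol 9.3.1.2 says that "participant enrollment for advanced metastatic cancer arms will be stopped" when the futility criterion is met, and places the monitoring in each metastatic arm. Protocol 9.3.1.3 applies the rules to the metastatic arms and gives operating characteristics for 40 CD8-high and 160 CD8-low participants. Table 14 is per arm and its first row is 20 evaluable participants.

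**Prostate safety.** Protocol 6.6.1.4 and SAP 4.4 contain an enrollment pause, a rule based on 4 or more of the first 5 participants in Prostate Cohort B, and a suspension trigger based on the count of treatment-related adverse events (TRAEs) requiring discontinuation. The 4-of-5 rule is justified by a beta(0.8, 1.2) prior, a 40% reference rate and a posterior probability above 80%.

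**Prostate sizes.** Protocol 9.1 plans about 20 CD8-low prostate participants: 5 per cohort, then 10 more in one of them. SAP 3 plans 10 per arm. Neither document gives a size for the prostate CD8-high arm.

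**The concern.** The scope sentence promises prostate participants two kinds of stopping rule that the text beneath it does not give them. For safety, the reader can find a different rule elsewhere. For futility there is nothing to find.

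This matters because, after the first 10 CD8-low prostate participants, the next 10 are assigned on tolerability alone (Protocol 6.3.1 and 6.6.1.4). If Cohort B is judged tolerable they receive a regimen that 6.6.1.4 describes as not extensively studied. The synopsis also says there is no independent data safety monitoring committee. An ethics board reading 9.3.1 or SAP 5.9 would reasonably believe that lack of activity is also being checked during this expansion. A statistician asked to run that check would have no boundary, no timing and no operating characteristics to work from.

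**Working it through.** **1. Reproduce the plan's own boundaries.** Inputs are from Protocol 9.3.1.1 and 9.3.1.2.

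- Toxicity: stop at the smallest x with Pr(θ > 0.40 | beta(0.8 + x, 1.2 + n − x)) > 0.975.
- Futility: stop at the largest x with Pr(θ < 0.20 | beta(0.4 + x, 1.6 + n − x)) > 0.975.

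At n = 20, 13 toxicities give 0.985 and 12 give 0.957, so the boundary is 13. One success gives 0.978 and two give 0.904, so the boundary is 1. Both match Table 14, and all 14 tabulated boundaries reproduce. Table 15 was checked at true toxicity rates of 0.10, 0.40 and 0.50, and agrees to rounding. For example, at toxicity 0.10 and response 0.20, stopping at 20 is 0.069 (stated 0.07) and stopping before 160 is 0.123 (stated 0.12). The metastatic rules are therefore sound as tabulated; the question is only their reach.

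**2. Compare the first look with the prostate sizes.**

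| Prostate unit | Planned size | Reaches 20 before accrual ends? |
|---|---|---|
| Expanded cohort (Protocol) | 5 + 10 = 15 | No |
| Other cohort (Protocol) | 5 | No |
| Each arm (SAP) | 10 | No |
| CD8-low group, both cohorts | about 20 | Only at completion |
| CD8-high arm | not stated | Cannot be judged |

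**3. Compare the prostate safety rule with 9.3.1.1.** Both use a beta(0.8, 1.2) prior and a 40% reference. At n = 5, Pr(θ > 0.40) is 0.776 for 3 events, 0.942 for 4 and 0.993 for 5. The 80% cut-off in 6.6.1.4 is passed at 4 and not at 3, as the protocol says. The 97.5% cut-off in 9.3.1.1 would need 5 of 5. The events also differ. Protocol 8.3.7 counts related adverse events leading to treatment discontinuation in the first 12 weeks. The 4-of-5 rule counts TRAEs leading to discontinuation of both agents in a 6-week first cycle. So 6.6.1.4 is a separate rule, not 9.3.1.1 applied to a smaller group.

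**4. What the futility formula would give at prostate sizes (illustration only).** With 0 successes the posterior probability is 0.970 at n = 8, 0.977 at n = 9, 0.983 at n = 10 and 0.995 at n = 15. There is no boundary up to n = 8, a boundary of 0 from n = 9 to 19, and a boundary of 1 at n = 20.

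For one look at 10, the chance of 0 successes is (1 − p)^10:

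- p = 5%: 0.95^10 = 0.60
- p = 10%: 0.90^10 = 0.35
- p = 20%: 0.80^10 = 0.11

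In a cohort of 15, at most 15 − 10 = 5 participants remain to be spared. The expected saving is at most 5 × 0.60 = 3.0 at 5% and 5 × 0.35 = 1.7 (1.75 before rounding the probability down from 0.349) at 10%. If the SAP's 10 per arm governs, the saving is 0.

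**The case against.** The strongest reply is that prostate monitoring was deliberately placed elsewhere. SAP 4.3 sends metastatic safety to 5.9 while SAP 4.4 handles prostate safety, and Protocol 8.3.7 points to 6.6.1.4. This stands. A reader might infer from the metastatic-only wording that prostate participants have no safety monitoring at all; 6.6.1.4 and SAP 4.4 contradict that for the combination cohorts.

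A second reply is that the monitored unit in 9.3.1 is the CD8 group, not the dosing cohort. This also stands: the CD8-low prostate group is about 20, so the first look equals its size rather than exceeding it. The look would still come too late to affect accrual. Nothing can be concluded for the CD8-high arm, whose size is not given.

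A third is that the probability statements are not tied to particular sample sizes, so they could be evaluated below 20. That is true of the formulas, but both are worded for metastatic arms.

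A fourth is that a small exploratory cohort needs no futility stop. SAP 5.4 says the study is not powered for hypothesis testing, and Protocol 9.1 describes the 15-participant cohort by credible intervals. This is a fair design choice, so the absence of a rule is not in itself the defect. A reader might also infer that adding a look at 10 would protect all ten expansion participants. It could spare at most 5, and fewer if enrollment continued while data mature: the first combination scan is at Cycle 2 Day 22, and stable disease counts as success only from 12 weeks. The 20% reference was set for metastatic arms, and 20% is the lowest conversion rate considered in Table 12.

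**Conclusion.** The point holds as an error of stated scope. Two documents claim Thall-method safety and futility monitoring for prostate participants; the rules supplied do not apply to them. For the combination cohorts the safety part of the claim is met by a different rule. The futility part is met by none. The consequence is a false assurance about the prostate expansion, not a flaw in the metastatic rules, which reproduce exactly.

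This rests on reading the metastatic wording in 9.3.1.1 to 9.3.1.3 as limiting, and on the planned sizes in Protocol 9.1 and SAP 3. The figures for a look at 10 further assume the protocol's 15-participant expanded cohort, independent outcomes, and the unchanged 20% reference and prior. They show what a rule would do and do not argue that one is needed.

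**What to change.** 1. In Protocol 9.3.1 and SAP 5.9, delete advanced prostate cancer from the scope sentence.
2. State that safety in the prostate combination cohorts is monitored under Protocol 6.6.1.4 and SAP 4.4, and that prostate has no futility stopping rule. Those sections set numerical rules only for the combination cohorts, so also say what, if anything, applies to the prostate CD8-high arm.
3. Qualify the sentence in Protocol 9.4 on success or futility in each subpopulation to match.
4. Reconcile Protocol 6.6.1.4 with SAP 4.4. They differ on the TRAE count that suspends enrollment (8 or more in either prostate cohort against 6 or more in the 5 mg/kg cohort), on the action after 4 of 5 (the next 10 assigned to Cohort A against suspension with ad hoc review), and on cohort sizes (15 and 5 against 10 and 10). The sponsor must decide which applies.
5. If a prostate futility look is intended, specify its unit, timing, definition of success, reference rate, boundary and operating characteristics, and whether enrollment pauses while data mature.

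Items 1 to 3 cost a few sentences in each document and remove no protection that exists now. Item 4 needs a sponsor decision and matching text. Item 5 carries a real trade-off: under the existing formula, a look at 10 has about an 11% chance of stopping a cohort whose true success rate is 20%.

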9.3.1.1 Safety Monitoring

For trial monitoring and decisions about future trials, TOX criteria are defined in [Section 8.3.7](#). A participant who voluntarily leaves the trial for any reason, including toxicity that does not meet the TOX criteria, will not count as having a TOX. Denote the probability of TOX by θ_T . The stopping rule for advanced metastatic cancer arms is given by the following probability statement: $\Pr(\theta_T > 0.40 \mid \text{data}) > 0.975$. That is, the trial will be stopped if, at any time during the study, it is determined that there is > 97.5% chance that the TOX rate is > 40%. The stopping rules assume a constant TOX rate for “standard therapy” of 0.40 ([Larkin et al, 2015](#); [Wolchok et al, 2017](#)) and a prior $\theta_T \sim \text{beta}(0.8, 1.2)$ for the current study. The stopping boundaries for this toxicity rule are to terminate the trial if the number of participants with TOX compared to the number of participants having received treatment exceeds the limits in [Table 14](#).

Table 14: Rules for Safety and Futility Monitoring per Arm

If there are this many (or more) participants evaluable for response	Stop the arm if there are this many (or more) participants with a TOX event:	Stop the arm if there are this many (or fewer) participants who meet the definition of success defined above:
20	13	1
40	23	3
60	32	6
80	41	9
100	50	12
120	59	15
140	68	19

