9.3.1.3 Joint Operating Characteristics for Safety and Futility Monitoring

The rules above will apply independently to each CD8 high or CD8 advanced metastatic cancer arm. It is estimated that there will be 40 participants with CD8 high tumors and 160 participants with CD8 low tumors in presenting the operating characteristics below. The probability of stopping at 20 participants provides the probability of stopping early in the CD8 high tumor group, assuming only 40 participants are entered. [Table 15](#) shows the operating characteristics under varying toxicity and response rates.

Table 15: Operating Characteristics Under Varying Toxicity and Response Rates

True Overall Toxicity Rate	True Overall Response Rate	Probability of Stopping at 20 Participants	Probability of Stopping Before 160 Participants	Median (25 th %ile, 75 th %ile) for “Cold” Cohort
0.10	0.05	0.74	>0.99	20 (20, 40)
	0.10	0.39	0.96	40 (20, 80)
	0.20	0.07	0.12	160 (160, 160)
	0.30	0.01	0.01	160 (160, 160)
	0.40	0.001	0.001	160 (160, 160)
0.20	0.05	0.74	>0.99	20 (20, 40)
	0.10	0.39	0.96	40 (20, 80)
	0.20	0.07	0.12	160 (160, 160)
	0.30	0.01	0.01	160 (160, 160)

True Overall Toxicity Rate	True Overall Response Rate	Probability of Stopping at 20 Participants	Probability of Stopping Before 160 Participants	Median (25 th %ile, 75 th %ile) for “Cold” Cohort
	0.40	0.001	0.001	160 (160, 160)
0.30	0.05	0.74	>0.99	20 (20, 40)
	0.10	0.39	0.96	40 (20, 80)
	0.20	0.07	0.12	160 (160, 160)
	0.30	0.01	0.01	160 (160, 160)
	0.40	0.002	0.002	160 (160, 160)
0.40	0.05	0.74	>0.99	20 (20, 40)
	0.10	0.40	0.96	40 (20, 80)
	0.20	0.09	0.19	160 (160, 160)
	0.30	0.03	0.09	160 (160, 160)
	0.40	0.02	0.08	160 (160, 160)
0.50	0.05	0.77	>0.99	20 (20, 20)
	0.10	0.47	0.99	40 (20, 60)
	0.20	0.19	0.78	80 (40, 140)
	0.30	0.14	0.75	80 (40, 140)
	0.40	0.13	0.75	80 (40, 160)

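### One sentence in protocol 9.3.1.1 states the toxicity boundary one event looser, and wider in scope, than the section's own posterior rule, Table 14 and Table 15

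*Protocol*

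**What the plan says.** Protocol 9.3.1.1 gives the toxicity rule for the advanced metastatic cancer arms in three forms.

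- **Posterior rule.** Stopping follows if, under a beta(0.8, 1.2) prior, "it is determined that there is > 97.5% chance that the TOX rate is > 40"%. The sentence that puts this into words says the trial stops.
- **Boundary sentence.** The instruction that refers the reader to Table 14 reads "terminate the trial if the number of participants with TOX compared to the number of participants having received treatment exceeds the limits in", with the table named next.
- **Table 14.** The table is titled as per arm. Its row index is "If there are this many (or more) participants evaluable for response" and its toxicity column reads "Stop the arm if there are this many (or more) participants with a TOX event". The limits are 13/20, 23/40, 32/60, 41/80, 50/100, 59/120 and 68/140.

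On scope, 9.3.1 monitors the CD8 high and CD8 low groups separately, and 9.3.1.3 says "The rules above will apply independently to each CD8 high or CD8 advanced metastatic cancer arm".

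The SAP does not restate these limits. SAP 4.3 points to SAP 5.9, which points back to protocol 9.3. The synopsis states that there is no independent data safety monitoring committee.

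**The concern.** The boundary sentence is the one place where prose tells the team how to use Table 14, and it disagrees with the table on three points.

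- **Inequality.** Exceeding 13 of 20 means 14. The table stops at 13.
- **Scope.** The sentence closes the trial. The table and 9.3.1.3 close one arm.
- **Denominator.** The sentence counts participants treated. The table counts participants evaluable for response. These two counts need not be equal on a given date.

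At stake is a safety threshold applied by the sponsor and investigators without an independent committee. A team that followed the sentence would be running a rule whose operating characteristics the protocol does not report. The CD8 high arm is the most exposed: 9.3.1.3 treats the look at 20 as its early-stopping look, assuming 40 participants, so a probability lost there is not recovered later.

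**Working it through.** **Inputs, all from the protocol.** Reference TOX rate 0.40, posterior cut-off 0.975 and prior beta(0.8, 1.2) come from 9.3.1.1. The success prior beta(0.4, 1.6) and the futility criterion ("there is > 97.5% chance that the CBR is < 20"%, again at 0.975) come from 9.3.1.2. Looks at 20, 40, …, 140 and the success limits 1, 3, 6, 9, 12, 15 and 19 come from Table 14. The comparison figures come from Table 15.

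**Step 1: which count first meets the posterior rule?** With x TOX events among n participants, the posterior is beta(0.8 + x, 1.2 + n − x). The limit is the smallest x for which Pr(TOX rate > 0.40) > 0.975.

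| n | Table 14 limit | Posterior at limit − 1 | Posterior at limit |
|---|---|---|---|
| 20 | 13 | 0.957 | 0.985 |
| 40 | 23 | 0.969 | 0.985 |
| 60 | 32 | 0.963 | 0.980 |
| 80 | 41 | 0.962 | 0.977 |
| 100 | 50 | 0.964 | 0.977 |
| 120 | 59 | 0.966 | 0.978 |
| 140 | 68 | 0.969 | 0.979 |

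At every look the printed limit is the first count above 0.975, so each limit is inclusive. The seven futility limits are reproduced in the same way, as the largest success count that meets their criterion. Read literally, *exceeds* would require 14, 24, 33, 42, 51, 60 and 69.

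**Step 2: which rule lies behind Table 15?** I used an exact joint binomial recursion over the seven looks, with TOX and success independent and the futility limits as printed. It was run once stopping at TOX ≥ limit and once at TOX > limit.

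| True TOX | Response | Quantity | Table 15 | ≥ limit | > limit |
|---|---|---|---|---|---|
| 0.50 | 0.40 | stop at 20 | 0.13 | 0.1320 | 0.0582 |
| 0.50 | 0.40 | stop before 160 | 0.75 | 0.7509 | 0.6781 |
| 0.50 | 0.30 | stop at 20 | 0.14 | 0.1382 | 0.0649 |
| 0.50 | 0.30 | stop before 160 | 0.75 | 0.7527 | 0.6806 |
| 0.50 | 0.20 | stop at 20 | 0.19 | 0.1917 | 0.1228 |
| 0.50 | 0.20 | stop before 160 | 0.78 | 0.7814 | 0.7176 |
| 0.40 | 0.40 | stop at 20 | 0.02 | 0.0215 | 0.0070 |
| 0.40 | 0.40 | stop before 160 | 0.08 | 0.0790 | 0.0455 |

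In the 18 of 25 Table 15 rows checked (all at TOX 0.10, 0.40 and 0.50; three at 0.30), the inclusive rule gives the printed stopping probabilities to rounding. The strict rule does not reproduce the rows above. In the three TOX 0.50 rows shown, it also moves the median number of participants from 80 to 100.

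One small residual: for TOX 0.50 and response 0.40, Table 15 prints a 75th percentile of 160 and the exact value is 140. The cumulative stopping probability at 140 is 0.7509, so this is a borderline case that simulation error would explain.

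**Step 3: single-look check.** With n = 20 and a true TOX rate of 0.50, P(X ≥ 13) = 0.1316 and P(X ≥ 14) = 0.0577. At a true rate of 0.60, which Table 15 does not cover, the corresponding figures are 0.4159 and 0.2500.

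**Step 4: scope and denominator.** No arithmetic applies. For scope, the word *trial* in the two sentences of 9.3.1.1 stands against the Table 14 title and header, 9.3.1, 9.3.1.3 and the futility text in 9.3.1.2, which closes enrollment on the arm. For the denominator, the posterior needs one n for both the events and the participants at risk of them, and the section names two.

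**The case against.** The best defence is that the section already settles the matter. The posterior statement in the same paragraph stops at 13 of 20, because the posterior there is 0.985. The boundary sentence supplies no number of its own and sends the reader to a table whose header states the inequality. Per-arm monitoring is stated repeatedly in both documents. To act at 14 of 20, a monitor would have to override the formal rule and the header.

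Much of this stands. It means that three stronger readings, each of which a reader might infer, are not supported:

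- **That the written rule as a whole is one event too lenient.** It is not. Only the boundary sentence is; the posterior rule and Table 14 agree with each other.
- **That Tables 14 or 15 are wrong.** The limits are reproduced exactly, and so are the stopping probabilities in the rows checked.
- **That a 50% TOX rate in the CD8 low arm carries a 0.75 chance of closing the CD8 high arm too.** That figure joins the sentence's trial-wide scope to the table's inclusive threshold. The same sentence taken literally throughout gives 0.68. Either figure also presumes that the CD8 high arm is still enrolling and that the repeated per-arm statements are ignored. It should not be used.

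The size should also not be generalised from one row. Stopping at 20 is more than halved at TOX 0.50, falls by about 40% at TOX 0.60 (0.42 to 0.25), and stopping before 160 moves only from 0.75 to 0.68.

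What the defence does not remove is that a safety instruction in the protocol, on its plain words, gives a different stopping count, scope and denominator from the rule that was evaluated. The SAP offers no second statement to check it against, and nobody should have to compute a beta posterior to learn which was meant.

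**Conclusion.** The point holds as an internal inconsistency confined to 9.3.1.1, with a clear numerical answer on the inequality: the posterior rule, Table 14 and Table 15 all describe stopping at the limit or above. On scope, the weight of the text is equally clear that the rule is per arm. On the denominator the documents do not settle which count is meant, and they do not give the gap between treated and evaluable participants, so its effect cannot be sized here.

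At TOX 0.50 and response 0.40, following the sentence literally costs 0.07 in the probability of stopping at 20 (0.13 to 0.06) and 0.07 in the probability of stopping before 160 (0.75 to 0.68). These figures assume looks at exactly 20, 40, …, 140, independent TOX and success, one n for both outcomes, and futility limits as printed. The sentence should be corrected because it states a safety threshold, but no design feature is in question.

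**What to change.** Bring the wording of 9.3.1.1 into line with the posterior rule and tables already there:

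1. Reword the boundary sentence along these lines: *stop the arm once its TOX count is equal to or greater than the Table 14 limit*.
2. In the preceding sentence, which puts the posterior statement into words, say that the arm is stopped rather than the trial.
3. Choose one denominator, treated or evaluable, define it for the toxicity rule, and use it in both the sentence and the Table 14 row header.

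The cost is a few words in one section and possibly one table header. The printed limits, the Table 15 probabilities and the sample size stay as they are. SAP 5.9 needs no edit, since it refers to protocol 9.3.
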